8.4.1 Baseline Data

All demographic and baseline characteristics will be summarized for the safety population.

The following variables will be summarized with frequent tabulations:

- Time since diagnosis (months)
- Baseline laboratory parameters: graded based on CTCAE

Descriptive statistics may also be used to summarize these variables.

8.4.2 Efficacy Analysis

All efficacy evaluations will be conducted using the efficacy population (Section 8.5).

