2.2 Secondary Objectives

- To evaluate efficacy by assessment of objective response rate (ORR) by RECIST v.1.1 in those with measurable disease
- To assess duration of response (DOR)
- To evaluate overall survival (OS)
- To evaluate the safety and tolerability of rucaparib

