3.2.2 Secondary Study Endpoints

The secondary endpoints include:

- Objective response will be scored per RECIST v.1.1 in those with measurable disease.
- Objective response rate (ORR) is defined as the proportion of patients who achieve a complete or partial response, as determined by RECIST v.1.1
- Duration of response (DOR) is defined as the time from first documentation of complete or partial response by RECIST v.1.1 to date of disease progression or death due to any cause. Responders who have not progressed will be censored on the most recent date that documents progression-free status.

CONFIDENTIAL

- Overall survival (OS) is defined as the time from start of study therapy to death due to any cause. Patients who are alive will be censored on the most recent date of patient contact.
- The incidence of adverse events (AEs), clinical laboratory abnormalities and dose modifications.

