4.1 Inclusion Criteria

Eligible patients must meet the following inclusion criteria:

- Histologically or cytologically confirmed diagnosis of pancreatic carcinoma with locally advanced or metastatic disease
- ≥ 18 years of age.
- Eastern Cooperative Oncology (ECOG) performance status of 0 to 1.
- Patients may have previously failed non-platinum containing therapy or may never have previously progressed on treatment.
- Patients must be on treatment with platinum-based (cisplatin, oxaliplatin or carboplatin) treatment for locally advanced or metastatic pancreatic cancer and have received a minimum of 16 weeks of therapy without evidence of disease progression based on the investigator's opinion.
 - Discontinuation of the platinum component of the regimen for chemotherapy-related toxicity is permissible provided the patient has previously received at least 16 weeks of platinum-based therapy without evidence of disease progression ≤ 8 weeks after treatment with the platinum agent

Patients may have received <16 weeks of platinum therapy if platinum was not able to be used for medical reasons or was medically required to be discontinued for legitimate reason in the opinion of the investigator (ie allergy, intolerable organ dysfunction)

- Documented deleterious BRCA1/2 or PALB2 mutation (germline or somatic) as assessed by CLIA certified laboratory. Variants that are considered to be non-detrimental ("Variants of uncertain significance", "Variants of unknown significance", "Variant, favor polymorphism" or "benign polymorphism" etc) are not sufficient for study entry.
- Measurable disease is not required for enrollment.
- Adequate organ function confirmed by the following laboratory values obtained ≤ 7 days prior to the first day of rucaparib:
 - (1) Absolute neutrophil count (ANC) $\geq 1.0 \times 10^9/L$
 - (2) Platelets $>100 \times 10^9/L$
 - (3) Hemoglobin $\geq 9g/dL$
 - (4) Aspartate aminotransferase (AST) and alanine aminotransferase (ALT) $\leq 3 \times$ upper limit of normal (ULN)
 - (5) Total bilirubin $\leq 1.5 \times$ ULN; if liver metastases or metabolic disorder such as Gilbert's syndrome, then $\leq 2.5 \times$ ULN.
 - (6) Serum creatinine $\leq 1.5 \times$ ULN or estimated glomerular filtration rate (GFR) ≥ 45 mL/min using Cockcroft Gault formula.

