8.2 Secondary Endpoints

The secondary endpoints are:

- (1) Objective response will be scored per RECIST v.1.1 as assessed by radiology review.
- (2) Objective response rate (ORR) is defined as the proportion of patients who achieve a complete or partial response, as determined by RECIST v1.1.
- (3) Duration of response (DOR) is defined as the time from first documentation of complete or partial response by RECIST v.1.1 to date of disease progression or death due to any cause. Responders who have not progressed will be censored on the most recent date that documents progression-free status.
- (4) Overall survival (OS) is defined as the time from start of study therapy to death due to any cause. Patients who are alive will be censored on the most recent date of patient contact.
- (5) The incidence of adverse events (AEs), clinical laboratory abnormalities and dose modifications.

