8.5 Subject Population(s) for Analysis

The following analysis populations are defined for the study:

Safety Population: The safety population will consist of all patients who received at least one dose of rucaparib.

Efficacy Population: The efficacy population will consist of all patients who received at least one dose of rucaparib and had a least one post-treatment assessment of response by RECIST v.1.1 (Appendix A).

9 Safety and Adverse Events

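### The documents give two conflicting denominators for ORR: patients with measurable disease in the objectives and endpoints, and a population without that condition in the statistical section

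*Combined protocol and SAP*

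**What the plan says.** **Objectives and endpoints.** The synopsis and section 2.2 set the secondary objective as "objective response rate (ORR) by RECIST v.1.1 in those with measurable disease". Section 3.2.2 repeats the limit in the endpoint itself: "Objective response will be scored per RECIST v.1.1 in those with measurable disease".

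**Eligibility.** Section 4.1 states "Measurable disease is not required for enrollment".

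**Statistical section.** Section 8.2 has nearly the same scoring sentence as 3.2.2, but with a different ending: "Objective response will be scored per RECIST v.1.1 as assessed by radiology review". It then says "Objective response rate (ORR) is defined as the proportion of patients who achieve a complete or partial response", with no condition on who those patients are. Section 8.4.2 says "All efficacy evaluations will be conducted using the efficacy population (Section 8.5" and makes no exception for ORR. Section 8.5 builds that population from patients who took at least one dose and "had a least one post-treatment assessment of response by RECIST v.1.1". No response-evaluable set is defined. The opening of section 8 adds that patients not evaluable for efficacy will be replaced. Section 8.4 plans ORR as an estimate with a 95% confidence interval.

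**Appendix B.** A partial response requires a fall of at least 30% in the summed diameters of target lesions, and target lesions are chosen from measurable lesions. A complete response is defined separately for nontarget lesions.

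**The concern.** An analyst who follows 3.2.2 divides by patients with measurable disease. One who follows 8.2, 8.4.2 and 8.5 literally divides by everyone in the efficacy population. The documents contain no rule of precedence between these sections. In an open-label, single-arm trial, the choice could then be made after the responses are known.

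Patients without measurable disease are plausible here. Entry normally follows at least 16 weeks of platinum without progression, and locally advanced disease is eligible. Under Appendix B, lesions below 10 mm are nonmeasurable, previously irradiated lesions are usually not measurable, and a primary with unclear borders should not be a target lesion.

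The efficacy population raises a second question. It omits treated patients who never had a post-treatment assessment. Some of these may be early failures, and none can be a recorded responder, so omitting them tends to raise the rate. What is at stake is whether the reported ORR answers the stated objective, and whether its denominator is fixed in advance.

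**Working it through.** **Figures in the plan.** The documents give no expected ORR, ORR threshold or ORR precision target, so there is no planned ORR figure to reproduce. The 81% power belongs to PFS6 and does not enter.

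**Notation.** Among treated patients, let *m* have measurable disease at baseline and *k* not. Let *u_m* and *u_k* be the numbers in each group without a post-treatment assessment. Let *R* be the responders with measurable disease and *c* the complete responses among patients without it.

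- Rate matching the objective, over all treated patients with measurable disease: A = R / m
- Rate from section 8 read literally: B = (R + c) / [(m − u_m) + (k − u_k)]

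**Step 1: measurable-disease effect alone.** Assume 42 analysed, everyone assessed (u_m = u_k = 0) and c = 0. Then B = R/42 = A × m/42. The documents do not give *m*, so it is shown as a range. Intervals are exact (Clopper-Pearson) 95%.

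| m (assumed) | A | B | m/42 |
|---|---|---|---|
| 42 | same as B | same as A | 1.00 |
| 38 | 8/38 = 21.1% (9.6 to 37.3) | 8/42 = 19.0% (8.6 to 34.1) | 0.90 |
| 34 | 7/34 = 20.6% (8.7 to 37.9) | 7/42 = 16.7% (7.0 to 31.4) | 0.81 |
| 28 | 6/28 = 21.4% (8.3 to 41.0) | 6/42 = 14.3% (5.4 to 28.5) | 0.67 |

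For scale, section 1.1 cites response rates of 22% and 16% for two PARP inhibitors in pancreatic cancer. Multiplied by m/42 for m = 38, 34 and 28, 22% becomes 19.9%, 17.8% and 14.7%, and 16% becomes 14.5%, 13.0% and 10.7%.

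**Step 2: nontarget complete responses.** Take m = 36 and R = 8, so A = 8/36 = 22.2%. With c = 0, B = 8/42 = 19.0%. With c = 1, B = 9/42 = 21.4%. With c = 2, B = 10/42 = 23.8%, which is above A. Whether such responses would count is itself unclear, because the best-overall-response table in Appendix B has no row for a patient without target lesions.

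**Step 3: unassessed patients.** With c = 0 and R > 0, B is below A only if its denominator exceeds *m*, that is, if k − u_k > u_m. If every patient has measurable disease (k = 0), B = R/(m − u_m), which exceeds A as soon as one treated patient is unassessed. With 42 treated, m = 34 and all 42 − 34 = 8 others assessed, eight unassessed patients with measurable disease would cancel the dilution exactly. If unevaluable patients are replaced until 42 are analysed, the literal denominator stays at 42 while the number treated rises, so the replacement rule also affects the comparison.

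The documents give none of *k*, *u_m*, *u_k* or *c*, so the sign of B − A cannot be determined from them.

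**The case against.** The strongest reply is that only a phrase is missing. The restriction appears three times, once in an endpoint definition, and 8.4.2 names an analysis set without fixing every endpoint's denominator. Duration of response shows this: it is confined to responders although 8.4.2 covers every efficacy evaluation. ORR could likewise be taken among efficacy-population patients with measurable disease. That reading is reasonable, but 8.2 does not state it, and it would still omit treated patients without an assessment.

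A reader might infer that the plan definitely computes ORR in the whole efficacy population because section 8 governs. No clause says so; the documents conflict, and the literal reading is one of two.

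A reader might also infer that patients without measurable disease can only lower the rate. Appendix B defines a nontarget complete response, and Step 2 shows that it can offset the dilution.

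Two further replies stand in part. Sampling error exceeds the gap: at m = 34 the rates differ by 20.6 − 16.7 = 3.9 points, while the interval around 7/34 runs from 8.7% to 37.9%. And ORR carries no test or decision rule. Both limit the consequence, but neither settles which denominator is intended.

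**Conclusion.** The inconsistency is real and nothing in section 8 resolves it. Applied literally, 8.2, 8.4.2 and 8.5 give an ORR that differs from the one in the objective whenever some patients lack measurable disease or some treated patients lack an assessment, unless the effects happen to cancel.

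The size is conditional. With 42 analysed, all assessed, and no complete response outside measurable disease, the difference is zero if all are measurable, about 2 points if 38 are, about 4 points if 34 are and about 7 points if 28 are. These values of *m* are assumptions.

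Two stronger conclusions are not supported. One is that ORR is biased downward under the plan: leaving out unassessed patients pulls the other way, and the net direction is unknown. The other is that a comparison with the earlier rucaparib rate of 16% would be distorted: no such comparison is planned, and section 1.1 notes that the earlier trial did not select for platinum sensitivity.

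ORR is a secondary estimate with a confidence interval. The primary PFS6 analysis is not affected by this point. The correction is worth making because it costs little and fixes one denominator before the data are read.

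**What to change.** - **8.2:** restore the measurable-disease restriction that 3.2.2 carries, in both the scoring line and the ORR definition.
- **8.5:** add an ORR set of all treated patients with measurable disease at baseline. Count those without a post-baseline assessment as non-responders.
- **8.4.2:** refer to that set for ORR, as an exception to the general rule.
- **Section 8, opening:** say how the set fits with the replacement of unevaluable patients, in particular that a treated patient with measurable disease who is replaced stays in the ORR denominator.
- **Reporting:** list any complete response in a patient without measurable disease separately, outside the ORR.

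Restoring the restriction resolves the contradiction. Counting unassessed patients as non-responders is a further step, which removes the exclusion of possible early failures from ORR.

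The cost is wording only, with no new data or visits. The denominator changes somewhat and the interval may widen slightly. In the m = 34 example, its width goes from 31.4 − 7.0 = 24.4 points to 37.9 − 8.7 = 29.2 points.

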8.4.3 Safety Analysis

All safety evaluations will be conducted using the safety population (Section 8.5).

8.5 Subject Population(s) for Analysis

The following analysis populations are defined for the study:

Safety Population: The safety population will consist of all patients who received at least one dose of rucaparib.

Efficacy Population: The efficacy population will consist of all patients who received at least one dose of rucaparib and had a least one post-treatment assessment of response by RECIST v.1.1 (Appendix A).

9 Safety and Adverse Events

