3.2 Study Endpoints

3.2.1 Primary Study Endpoints

The primary study endpoint will be the PFS rate at 6 months (PFS6) as determined from a Kaplan-Meier curve. PFS defined as the time from start of study therapy to the occurrence of disease progression according to RECIST v1.1, as assessed by the investigator, or death from any cause. Patients who are alive and progression-free will be censored on the most recent date that documents progression-free status (i.e. scan date or clinic visit date).

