^m = Disease assessment to include clinical examination, and appropriate imaging techniques, including CT scans of the chest, abdomen and pelvis, with appropriate slice thickness per RECIST; other studies (MRI, X-ray, PET, and ultrasound) may be performed if required. The same method used to detect lesions at baseline are to be used to follow the same lesions throughout the clinical study. If a patient has known brain metastases, this disease should be evaluated at each required assessment.

ⁿ = Tumor scans to be performed within 7 days prior to start of every odd numbered cycle, ie prior to start of Cycle 3, Cycle 5, Cycle 7, etc. A confirmatory scan should be performed ≥ 4 weeks after an initial response of PR or CR is observed.

^o = End of treatment CT scans should be performed if treatment was discontinued for reason other than radiologic disease progression.

^p = If CT scans were not performed at End of Treatment or within 28 days prior to End of Treatment, a CT scan should be performed at the 28-day follow-up visit.

^q = Archival tumor tissue, if available, will be collected and stored. (Note: This sample is not required to be submitted on Cycle 1, Day 1, but should be submitted as soon as possible after a patient begins treatment with rucaparib).

^r = A screening tumor biopsy will be collected if deemed safe and feasible. A biopsy will be collected if the reason for discontinuation was radiologic disease progression.

CONFIDENTIAL

^s= All patients discontinued from treatment, regardless of reason, should be followed for survival every 8 weeks until death, loss to follow-up, withdrawal of consent from study, or closure of the study. Follow-up can be performed via telephone.

^t= Up to 50cc of whole blood to be collected in 4 total tubes, likely to include EDTA and Streck tubes. Refer to laboratory manual for details. *If a patient has been on for >12 cycles, stop collecting serial ctDNA until progression or concern for progression.

^u= Patients will have coagulation tests PT/PTT/INR in advance of the clinical trial biopsy

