7.10.2 Tumor Tissue Analysis

Paired Tumor Biopsies: Tumor tissue biopsies will be obtained during screening and at time of disease progression, as deemed safe and feasible. It will be stored at an internal facility (refer to Lab Manual) to be used for analysis at a later date. Analysis may include:

- DNA extraction and sequencing in order to identify mutations in HR pathway genes, and evaluate whether a patient has a reversion mutation or other mutation(s) that may be associated with response or resistance to rucaparib.
- Analysis of genomic structural variation to determine a signature that may correlate with response or resistance to rucaparib.
- Additional or alternate assays depending on tissue availability and available technology.

Organoids: If feasible, organoids of tumor tissue will be created at the University of Pennsylvania and analyzed for genetic concordance with the parent samples. Other analyses may be conducted depending on practical constraints.

CONFIDENTIAL

This material is the property of the University of Pennsylvania.

Archival Tumor Tissue: If available, archival tumor tissue should be located during the screening process and submitted as soon as possible after a patient begins rucaparib.

Additional Tissue: If additional tissue or blood is available, it may be sent to Clovis Oncology for genetic analysis using the Foundation One platform or an alternative platform.

8 Statistical Plan

This is a single arm single stage Phase II study to evaluate progression-free survival rate at 6 months (PFS6) in 42 eligible patients. Patients who are not evaluable for efficacy, as defined within the protocol, will be replaced. Enrollment is expected to continue for 42 months and follow-up will continue for 6 additional months, prior to the final analysis of PFS. The null hypothesis is that the PFS6 rate is 44% (same as reported for standard therapies) and the alternative hypothesis is that the PFS6 rate has been increased to 60%.

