8.1 Primary Endpoint

The primary study endpoint will be progression-free survival (PFS), defined as the time from start of study therapy to the occurrence of disease progression according to RECIST v1.1, as assessed by the investigator, or death from any cause. Patients who are alive and progression-free will be censored on the most recent date that documents progression-free status (ie., scan date or clinic visit date). The PFS6 will be estimated from the Kaplan-Meier curve.

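### A treated patient who dies before any post-treatment RECIST assessment is left out of PFS6 and OS, although the death is an event for both; each such death biases the results upward

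*Combined protocol and SAP*

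**What the plan says.** - **Analysis set.** Section 8.4.2: "All efficacy evaluations will be conducted using the efficacy population (Section 8.5"). Section 8.5 defines that population as "all patients who received at least one dose of rucaparib and had a least one post-treatment assessment of response by RECIST v.1.1". The only other set, the safety population (at least one dose), is assigned to safety analyses in Section 8.4.3.
- **Replacement.** The opening paragraph of Section 8: "Patients who are not evaluable for efficacy, as defined within the protocol, will be replaced".
- **Endpoints.** Section 8.1 times PFS from start of study therapy to RECIST progression "as assessed by the investigator, or death from any cause". Section 8.2: "Overall survival (OS) is defined as the time from start of study therapy to death due to any cause". Under Section 3.2.1, patients alive and progression-free "will be censored on the most recent date that documents progression-free status".
- **Scan timing.** Section 6.1, note n: "Tumor scans to be performed within 7 days prior to start of every odd numbered cycle". The first such cycle after baseline is Cycle 3. Note o adds: "End of treatment CT scans should be performed if treatment was discontinued for reason other than radiologic disease progression". Note p and Sections 3.1.4, 6.7 and 7.8.1 provide a 28-day follow-up scan when the end-of-treatment scan was not done.
- **Decision rule.** Section 8.4: PFS6 is estimated by Kaplan-Meier, and the trial succeeds if the lower limit of the two-sided 95% interval lies above 44%. The type of interval is not stated.

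**The concern.** Whether a patient enters the efficacy population depends on something that happens after treatment starts, and death can prevent it. For response rate, a requirement for a post-baseline assessment can be argued. For PFS and OS it cannot, because no scan is needed to know that a patient who has died has had the event.

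If such deaths occur, the quantity estimated is PFS6 among patients who lived to be scanned, not PFS6 from start of therapy as Sections 3.2.1 and 8.1 define it. It is then tested against 44%, a benchmark that the documents do not describe as restricted in this way. There is no control arm to share the exclusion.

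**Working it through.** **When the exclusion can operate.** With 28-day cycles, Cycle 3 Day 1 is day 57 (2 × 28 + 1), so the first scheduled scan falls on days 50 to 56. A death before then, without an unscheduled or end-of-treatment scan, leaves the patient outside the set. No section brings the patient back, and no all-treated efficacy analysis is planned.

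**The plan's own figure.** Section 8.4 gives 81% power for 44% versus 60% with 42 patients, 42 months of accrual, 6 months of follow-up and exponential survival. The hazards are −ln(0.44)/6 = 0.1368 and −ln(0.60)/6 = 0.0851 per month, with 38.8 and 35.1 expected events. Power is 80.3% on the log-hazard scale, Φ(√35.1 × 0.4745 − 1.96), and 81.5% on the survival scale with null and alternative variances. The 81% reproduces. It takes no account of the exclusion.

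**Inputs for the bias.** n = 42, null 44% and alternative 60% come from Section 8.4. Let d be the number of treated patients who die unscanned and are replaced. The documents give no value; I show 0, 1 and 2. I assume no censoring before 6 months, so Kaplan-Meier PFS6 is x/42, with x the number progression-free at 6 months.

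**Shift in the estimate.** 42 + d patients are treated and 42 analysed, and all d are failures, so reported PFS6 = p × (42 + d)/42.

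**Success thresholds at n = 42.**
- Plain interval: 24/42 has lower limit 42.2% (fail) and 25/42 has 44.7% (success).
- Log-log interval with Greenwood variance: 25/42 has 43.2% (fail) and 26/42 has 45.5% (success).

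The false-positive chance is P(X ≥ 25) for plain or P(X ≥ 26) for log-log, with X binomial(42, reported rate) when the true rate is 44%. The nominal upper tail of the two-sided 5% test is 2.5%.

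| d | True 44% reads | True 60% reads | False positive, plain | False positive, log-log |
|---|---|---|---|---|
| 0 | 44.0% | 60.0% | 3.1% | 1.5% |
| 1 | 45.0% | 61.4% | 4.2% | 2.1% |
| 2 | 46.1% | 62.9% | 5.6% | 2.9% |

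The 3.1% and 1.5% at d = 0 come from the interval type, not from the exclusion.

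**Could the conclusion change?** Put the deaths back and keep the replacements:
- Plain: 25/42 (44.7%, success) becomes 25/43 (43.4%, fail). One step above the threshold, 26/44 still succeeds (44.6%).
- Log-log: 26/42 (45.5%, success) becomes 26/43 (44.3%, success), then 26/44 (43.2%, fail). One step above the threshold, 27/44 still succeeds (45.4%).

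**If the patient is dropped but not replaced.** The bias remains. Under log-log, 25/42 fails at 43.2%, while 25/41 succeeds at 44.4%.

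**OS.** With exponential OS and k early deaths dropped from 42, the median lengthens by the factor ln(2/(1 − k/42))/ln 2, which is about 1.03 for k = 1 and 1.07 for k = 2. An observed median moves in steps and may not change for a single exclusion.

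**The case against.** **Few patients will be affected.** Section 4.1 requires ECOG 0–1 and, with stated exceptions, at least 16 weeks of platinum-based therapy without progression; Section 4.2 excludes life expectancy under 12 weeks. Living patients who stop early should be scanned at end of treatment or at 28 days, and Appendix B asks for progression to be documented after symptomatic deterioration. This stands: the number is probably small and may be zero. None of these provisions helps a patient who has already died.

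**The replacement link is an inference.** Section 8.5 does not use the word evaluable, and Appendix B uses not evaluable as a response category. That category is not a patient-level replacement rule, and Section 8.5 is the definition that fits. If the link is rejected, Sections 8.4.2 and 8.5 still exclude the patient.

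**OS is not named in Section 8.4.2.** True, and the objectives list it apart from response rate. But it is a survival endpoint and no other set is assigned to it.

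**The direction is not always favourable.** For unscanned deaths it is. For a living patient with no post-treatment scan the effect can go either way; dropping a long survivor would lower OS.

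**The inflation is modest.** Under log-log, one replaced death leaves the error at 2.1%, below 2.5%. Under plain, the error is already 3.1% with no deaths, so the unstated interval type matters about as much.

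**Conclusion.** The concern holds. As written, the plan discards deaths that its own endpoint definitions count as events, and each one can only raise the Kaplan-Meier estimate. With replacement, the shift per death is about 1.0 point at a true PFS6 of 44% and 1.4 points at 60%. With one or two such deaths, the trial's conclusion is exposed only at the success threshold itself: one death suffices under a plain interval, two under log-log.

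These sizes rest on an assumed number of deaths, no censoring before 6 months, and Section 8.5 being the definition meant by the replacement rule. The direction needs only that such a death occurs. It should be fixed, since the correction costs little and choosing the set after results are known would be open to challenge.

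**What to change.** - **Sections 8.4.2 and 8.5:** make all patients who received at least one dose the primary set for PFS6, PFS and OS. State that a death before the first post-treatment scan is an event on its date. Censor living patients without a RECIST assessment by the existing rule in Sections 3.2.1 and 8.1.
- **Section 8, opening paragraph:** limit replacement to patients who never received rucaparib.
- **Supportive analysis:** keep the RECIST-assessed set, labelled as such.

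**Cost.** Wording only, with no new data. The primary set becomes the 42 treated patients, and the supportive set may be smaller. A treated patient who withdraws within days is no longer replaced and contributes little follow-up; the same bar on replacement applies to one later found ineligible. The expected estimate falls by the 1.0 to 1.4 points per unscanned death that the exclusion had added.

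Because the set stays at 42, one death reverses a threshold result only if the replacement would have been progression-free at 6 months: plain 25/42 becomes 24/42 (42.2%), and log-log 26/42 becomes 25/42 (43.2%). Otherwise the result is unchanged.
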